Mini-International Neuropsychiatric Interview (MINI), Version 7: The MINI is a brief structured interview that was designed to assess DSM 5 diagnoses using a series of questions in dichotomous format (yes/no). Earlier studies have found that the MINI is similar in sensitivity, specificity, and inter-rater reliability to other more lengthy diagnostic interviews, such as the SCID-I/P (Sheehan et al., 1998).

Childhood Trauma Questionnaire (CTQ): Since childhood trauma has been shown to affect corticolimbic brain activity (Dannlowski et al., 2012) and corticolimbic brain activity following OT administration (Fan et al., 2014) we will use the CTQ to assess childhood trauma exposure in each of the study participants (D. P. Bernstein et al., 1994; D. P. Bernstein, Fink, L.A., 1998). The CTQ is a 25-item self-report questionnaire used to assess the extent to which individuals have childhood abuse and neglect. Subjects answer each question using a 5-point Likert scale ranging from (1) never true to 5 (very often true). The reliability and validity of the CTQ have been tested in both healthy and substance-dependent populations (D. P. Bernstein et al., 1994; D. P. Bernstein, Fink, L.A., 1998; Carpenter et al., 2007; Hyman et al., 2008; Hyman et al., 2007).

Within Session Rating Scale: A modification of the Within Session Rating Scale (Childress et al., 1986) will be used to assess craving and mood during the procedures. This scale is anchored with the adjectival modifiers ("not at all and extremely"). There are four items assessing domains of craving (want/need/craving/ability to resist). For the market value item, the individual will be asked to name the dollar amount they would be willing to pay for cocaine if they could have it "now". Other items include anxiety and mood. These data will be collected prior to treatment, prior to MIST1, and immediately after each run of the MIST.

Menstrual History Diary: Drug craving mood and affect have been associated with menstrual cycle phase and ovarian hormone status (Kirschbaum et al., 1999; Sinha et al., 2007). Subjects will be asked to estimate the timing of their cycle for the 90-days prior to study entry and to track their cycle during study participation.

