Power and sample size estimates for Hypotheses 1A and 1B were based on pilot data from the MIST (see Preliminary Studies). Based on these data we expect a between group difference (CD-PBO vs. HC-PBO) in the PPI beta estimate of OFC-amygdala connectivity of $\Delta=3.6$ with a RMSE=4.0 ($d = 0.9$) (Cohen, 1988). Assuming an effect similar to the pilot data, the total effective sample size would be 40 subjects per group to provide 80% power for a between groups study design with a type I error rate of 0.05.

Power and sample size estimates for Hypothesis 1C were based on data from a double-blind placebo controlled pilot study of OT on stress reactivity to the Trier Social Stress Task in CD subjects. Based on these data we expect a between group difference in cocaine craving following the MIST of $\Delta=8.24$ with a RMSE=11.03

($d=0.75$) (Cohen, 1988) and a subjective anxiety difference of $\Delta=1.07$ with a $RMSE=2.20$ ($d=0.49$). As in the oxytocin pilot study, participants will be assessed at five time points (m), with an anticipated intraclass correlation coefficient of 0.78 for both craving and anxiety outcomes ($ICC=0.78$ & 0.79, respectively). The design effect, which accounts for the multiple correlated observation within each subject, is estimated to be 4.12 ($DE= [1+(5-1)0.78]$) (Donner and Klar, 2000). Assuming independent observations and an effect similar to the pilot data for the anxiety response ($d=0.48$), the total effective sample size would be 140 subjects (35 CD and 35 controls per treatment arm) to provide 80% power with a type I error rate of 0.05. In a clustered setting, the sample size is $N_{\text{effective}} = nm/DE$ where n is the number of participants required when m replications within participants are performed after accounting for the design effect (DE). For the study at hand, the total number of participants required is therefore estimated to be $N=135$ ($=140*4/4.12$), As such, our proposed sample size of 160 subjects (40 CD and 40 HC per treatment arm) should provide sufficient statistical power to detect the planned anxiety and craving responses to the MIST. To account for an estimated attrition rate of 45%, we will enroll 210 participants in order to complete 160 scans.

Specific Aim 2

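### The Hypothesis 1C participant number (N=135) inverts the plan's own design-effect formula and mixes 4 with 5 time points; the stated formula and inputs give 116

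*Combined protocol and SAP*

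**What the plan says.** All the ingredients are in Power and Sample Size, Specific Aim 1, in the text on Hypothesis 1C.

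- Time points: "participants will be assessed at five time points (m").
- Correlation: "an anticipated intraclass correlation coefficient of 0.78 for both craving and anxiety outcomes", followed by 0.78 and 0.79 for the two outcomes separately.
- Design effect: 1 + (5 − 1) × 0.78 = 4.12.
- Effective size: 140 in total (35 cocaine-dependent and 35 control participants per treatment arm), for "an effect similar to the pilot data for the anxiety response ($d=0.48"), "to provide 80% power with a type I error rate of 0.05".
- Formula: N_effective = nm/DE, "where n is the number of participants required when m replications within participants are performed after accounting for the design effect (DE").
- Result: "the total number of participants required is therefore estimated to be $N=135$ ($=140*4/4.12").

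The next sentence draws from this result that 160 participants, 40 per cell, are enough for the anxiety and craving outcomes.

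The rating schedule is described in two ways. The Within Session Rating Scale entry in Assessments (C3e) says "These data will be collected prior to treatment, prior to MIST1, and immediately after each run of the MIST", which with three runs is five ratings. Specific Aim 1 and the Overview (C3a) mention a baseline rating and one after each run, which is four. Under Hypothesis 1C, the Statistical Methods section enters baseline values as covariates.

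**The concern.** The plan gives a formula, gives every input, and then prints a number that the formula does not produce. The figure of 140 is the effective size, the left-hand side of the formula, but the calculation puts it in the place of n. A higher within-person correlation then lowers the number of people required, which is the opposite of what a design effect does. The numerator also uses 4 while the denominator was built with 5.

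This matters because 135 is the only figure that links the effective size to the claim that 160 is sufficient for anxiety and craving, which the Summary of the Protocol (5.1) lists among the primary outcomes. A later recalculation that copied the printed operation would carry the error forward.

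**Working it through.** **1. Reproduce the plan's inputs.** The plan does not say whether the 0.05 is one- or two-sided. Two-sided, with 80% power and d = 0.48, the normal approximation gives 2 × (1.960 + 0.842)² / 0.48² = 68.1, so 69 per arm. The t-based calculation gives 69.1, so 70 per arm and 140 in total, which matches. (One-sided would give 54 per arm, so two-sided is the reading that fits.) The pilot figures give 1.07/2.20 = 0.486, printed as 0.49 in one place and 0.48 in another; the 140 goes with 0.48. The design effect 1 + 4 × 0.78 = 4.12 also matches.

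**2. Reproduce the printed result.** 140 × 4/4.12 = 135.9, printed as 135. The number and its expression agree with each other, so this is not a misprint in one of them.

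**3. Solve the plan's formula for n.** From N_effective = nm/DE, n = N_effective × DE/m.

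| Reading | DE | n |
|---|---|---|
| m = 5, ICC 0.78 (as stated) | 4.12 | 140 × 4.12/5 = 115.4, so 116 |
| m = 5, ICC 0.79 (the anxiety value) | 4.16 | 140 × 4.16/5 = 116.5, so 117 |
| m = 4 throughout, ICC 0.78 | 3.34 | 140 × 3.34/4 = 116.9, so 117 |
| m = 3 (post-run ratings only), ICC 0.78 | 2.56 | 140 × 2.56/3 = 119.5, so 120 |
| m = 4 in n but 5 in DE (inconsistent) | 4.12 | 140 × 4.12/4 = 144.2 |

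Check of the first row: 116 × 5/4.12 = 140.8, which meets 140. None of these readings gives 135.

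**4. Test the two operations at the extremes.** With an ICC of 1, repeat ratings add nothing, so 140 people are needed. The correct operation gives 140 × 5/5 = 140; the printed one gives 140 × 4/5 = 112. With an ICC of 0, five ratings count as five independent observations. The correct operation gives 140 × 1/5 = 28; the printed one gives 140 × 4/1 = 560.

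**5. Size of the error.** The printed 135 exceeds the consistent figures by 15 to 19 participants: 15/120 = 12.5% to 19/116 = 16.4%.

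**6. What 160 provides on the pooled basis.** 160 × 5/4.12 = 194.2 effective, or 97.1 per treatment arm. At d = 0.48 that gives about 92% power (two-sided 0.05, normal approximation).

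**7. What it provides for the contrast that Hypothesis 1C names.** The hypothesis compares cocaine-dependent participants on oxytocin with cocaine-dependent participants on placebo, 40 against 40. Seventy effective per arm needs 70 × 4.12/5 = 57.7, so 58 per arm. Forty per arm gives 40 × 5/4.12 = 48.5 effective. For anxiety, 0.48 × √(48.5/2) − 1.96 = 0.40, which is about 66% power. For craving at the plan's d = 0.75, the same calculation gives about 96%.

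**The case against.** The strongest reply is that the error is conservative. Every consistent reading gives fewer participants than 135, so the plan's conclusion that 160 is enough survives on its own pooled basis and gains margin. That is right, and it limits the point to a correction of the derivation.

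A second reply is that the 4 may be deliberate. The Overview describes four ratings, or the pre-treatment rating may have been set aside because baseline is a covariate. That is possible, and it is a reason not to treat 116 as the only answer. It does not rescue 135: a deliberate 4 would also belong in DE, and the result would then be 117.

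Two stronger readings are tempting, and the documents support neither.

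- A reader might put the stated m of 5 into the printed expression, obtain 140 × 5/4.12 = 169.9, and infer that 160 is too few. That figure arises only if the inversion is kept while the other slip is repaired. No valid use of the plan's formula gives it.
- A reader might take the lower figure of 116 as showing that Hypothesis 1C is comfortably powered. The 140 counts both populations in each treatment arm, whereas the hypothesis concerns the cocaine-dependent participants only.

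**Conclusion.** The stated N=135 is wrong as derived: it inverts the plan's formula and combines two values of m. The formula and inputs as stated give 116. The figure is 117 with m = 4 throughout or with the anxiety ICC, and 120 if only the three post-run ratings count as outcomes. The printed number is about 13–16% above these.

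The error overstates the requirement, so it does not undermine 160 for oxytocin against placebo pooled over both populations. This rests on the plan's own d of 0.48, ICC of 0.78 to 0.79 and a two-sided 0.05, and on its treatment of repeated ratings as exchangeable replicates of one treatment effect. A rating taken before treatment cannot carry that effect, so the readings with fewer outcome ratings deserve weight.

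Neither 116 nor 135 establishes power for the contrast within the cocaine-dependent group. For anxiety the same formula asks for 58 per arm against 40 planned, and 40 gives about 66% power. That shortfall comes from the pooling behind the 140, not from the arithmetic slip.

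**What to change.** In Power and Sample Size, Specific Aim 1, replace the sentence that gives N=135 with n = N_effective × DE/m. Use one value of m, the number of ratings analysed as outcomes, in both DE and n. Reconcile that number with the two descriptions of the rating schedule and with the use of baseline as a covariate.

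Restate N as 116 (140 × 4.12/5) if all five ratings are outcomes, or as 117 to 120 if the baseline or pre-task ratings are not. Round up.

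Add one sentence saying that the figure refers to oxytocin against placebo pooled over cocaine-dependent and control participants. It should also say that the power for Hypothesis 1C's own contrast is about 66% for anxiety at 40 per arm on the same inputs.

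The cost is protocol wording and one recalculated figure. This correction does not require a change to enrolment.

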NCT#02682784

Title: Neural substrates of emotion: Impact of cocaine dependence

Document Date: 06/18/2020

NEURAL SUBSTRATES OF EMOTION: IMPACT OF COCAINE DEPENDENCE

SPECIFIC AIMS

Over one million individuals in the United States meet criteria for cocaine use disorders. Relapse rates are highest among cocaine-dependent (CD) populations. Social stress is a significant risk factor for relapse. Data from human neuroimaging studies suggest that “top-down” prefrontal cortical inhibition of amygdala activity controls emotional responses to social stimuli. A growing literature suggests that hypoactivity in the medial prefrontal cortex coupled with increases in amygdala activity underscore the vulnerability of CD individuals to relapse. Neuroimaging studies of corticolimbic network activity (functional connectivity) have been conducted in CD subjects at rest. Compared with healthy controls, CD subjects exhibited lower corticolimbic connectivity and the degree of corticolimbic uncoupling was associated with time to relapse. Studies measuring corticolimbic connectivity during exposure to a social stress task in CD subjects could provide critical insight into the neurobiologic mechanisms that underscore the sensitivity of CD individuals to social stress. Moreover interventions that improve corticolimbic connectivity in CD subjects may be effective therapeutic strategies for preventing relapse in CD populations. Oxytocin (OT) is an anxiolytic neuropeptide that attenuates amygdala responses to aversive social cues. In order to better understand the neurobiologic mechanisms that control emotion-related behavior in CD populations, we propose a double-blind placebo (PBO) controlled study using blood oxygen level dependent (BOLD) functional magnetic resonance imaging (fMRI) to measure (1) corticolimbic functional connectivity during the Montreal Imaging Stress Task (MIST) and (2) amygdala activity in response to an implicit facial affect recognition paradigm in groups of CD individuals (CD n=80) and healthy non-dependent controls (HC, n=80). Prior to the scanning session, participants will receive either intranasal OT (24 IU) or PBO spray (n=40 per treatment group). The order of the tasks will be counterbalanced.

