The primary objective of this proposal is to identifying the neurobiologic substrates of emotion-related behavior in CD individuals. After the initial screening and assessment visit, an fMRI study visit will be scheduled (Figure 4). The study will use a double-blind placebo-controlled design. Prior to the scan, participants will receive either intranasal OT (24 IU) or a placebo (PBO) spray. During the scan, BOLD fMRI data will be acquired while the participants perform a series of stressful and non-stressful mental arithmetic challenges (Dedovic et al., 2005). Performance feedback will be provided by the MIST software in real-time and also by the investigator. Participants will complete three runs of the MIST. Subjective responses (anxiety and craving) will be collected at baseline and immediately after each run of the MIST. Participants will also complete an implicit facial affect recognition task. Since the amygdala may habituate to the stress tasks, the order of the tasks will be counterbalanced. At the end of the study visit, subjects will be debriefed, compensated and discharged.

C3b. Participants

Subjects will be men and women of all racial and ethnic groups aged 18-65. A total of 160 study participants will be recruited: (1) cocaine-dependent individuals (CD, n=80); and (2) healthy control subjects free of major Axis I diagnoses (HC, n=80). Gender differences in the neural correlates of stress have been found in fMRI studies of HC and CD individuals (Li et al., 2005; Potenza et al., 2012), and in amygdala responses to fearful faces following intranasal OT administration (Domes, Heinrichs, Glascher, et al., 2007; Domes et al., 2010). Based on our experience in recruiting CD subjects for clinical studies, we expect that 15-20% of the subjects will be female. Differential recruitment will be used as needed to ensure that 15-20% of the participants in each study

group are female. Groups will also be matched on age, smoking status, and education. On a monthly basis, we will assess the status of each group in terms of core variables and tailor recruitment

Figure 4. Overview of Study Visit Procedures

accordingly. This has worked well in all of our previous clinical research studies.

C3c. Recruitment and Retention

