Preprocessing: Post-acquisition preprocessing and statistical analysis of all of the neuroimaging data will be performed using FEAT (FMRI Expert Analysis Tool) Version 5.98, part of FSL (FMRIB's Software Library, www.fmrib.ox.ac.uk/fsl). Functional magnetic resonance imaging (fMRI) blood oxygen level dependent (BOLD) imaging data will be acquired using a standard multi-slice gradient echo planar imaging sequence (TR=2200 ms, TE=35 ms, 64 x 64 matrix, 3 mm isotropic voxels, 271 volumes). Data will be preprocessed using scripting tools from FMRI Expert Analysis Tool (FEAT) Version 5.98, part of FMRIB's Software Library (FSL; www.fmrib.ox.ac.uk/fsl). First non-brain signal will be removed using FSL's BET brain extraction. Scans will be corrected for motion using FSL's linear registration and scans will be spatially smoothed using a Gaussian kernel of 8 mm FWHM. Since head motion can impact functional connectivity analyses, participants with head motion exceeding 0.2 mm will be excluded from the analyses (Power et al., 2012). The "fsl_motion_correction" scripting tool will be used to identify and scrub motion artifacts from each participant's data (Power et al., 2013). Scans will be spatially co-registered with a standardized anatomical template (Montreal Neurological Institute) using a 12 parameter affine transformation (Rorden et al., 2000). **Analysis:** Functional connectivity will be measured using a PPI based approach (Friston et al., 1997). A customized square wave form representing the task (1 = stress condition and -1 = control condition) and the duration of each condition will be convolved with a double-gamma hemodynamic response function. A mask of the seed region will be made using a 12-mm diameter sphere located in the center of the left amygdala using the MNI coordinates (x, y, z = -22, 0, -22). The transformation parameters described above will also be applied to the mask. For each participant and each run of the MIST, the mean corrected and high pass filtered time series of the BOLD signal in the left amygdala will be extracted and used in a single subject whole brain PPI analysis. The PPI model will include (1) the task vector; (2) the time series of the BOLD signal in the left amygdala; (3) a term representing the positive task x seed interaction; and (4) a term representing the negative task x seed interaction. The first level analysis will generate contrast images of the parameter estimates for each of the four regressors. Since the hypotheses associated with Specific Aim 1 explore increases in amygdala - prefrontal cortical connectivity in response to social stress, the group analysis will focus on the positive interaction term. The contrast images of the parameter estimates of the positive interaction term will be entered into a 2nd-level random effects analysis. Unpaired t-tests will be used to test for the following group differences (Hypothesis 1A: CD-PBO vs. HC-PBO) and (Hypothesis 1B: CD-OT vs. CD-PBO). Analyses will be conducted using FMRIBs Local Analysis of Mixed Effects (FLAME 1). Additional analyses comparing (HC-OT vs. CD-OT) will be conducted using an unpaired t-test and applying the appropriate corrections for multiple tests. We will also conduct an exploratory gender analysis between the CD and HC women in the four groups (Domes, Heinrichs, Glascher, et al., 2007; Domes et al., 2010; Potenza et al., 2012). We anticipate that 15-20% of the subjects in each group will be female (n=6/8 per group). We

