Power and sample size estimates were based on the literature. Neuroimaging studies of patients with PTSD and trauma matched controls have found significant group differences in the BOLD signal change in the amygdala during implicit facial affect processing. Based on data from these studies the appropriate effect size for our study ranges between 1.2-1.4 (Felmingham et al., 2010; Rauch et al., 2000). To detect an effect size (f) of 1.2 with a type 1 error protection level of .05 and $n=19$ will have power ($1-\beta$) of .95 (Cohen, 1988). As such, our proposed 40 participants per group should provide sufficient statistical power to detect group differences in the BOLD signal change in the amygdala during implicit facial affect processing.

C3g. Design Considerations

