The REDCap Study Database Version 4, supported by the South Carolina Clinical and Translational Research Institute (SCTR) at MUSC, will be used to capture data directly into an online database (Harris et al., 2009). Auditing will occur quarterly by comparing a random sample of 10% of participant's original datasheets to the values entered for those individuals in all data files. All of the neuroimaging data are automatically transferred to servers managed by CBI. Data will be stored on CBI password protected servers which receive daily data backups.

C3i. Operational Plan and Research Timetable

The first four months of the grant will be used for obtaining regulatory approvals, training and in-servicing CTRC staff and database creation. We have on-going trials involving CD and healthy control populations, thus we have trained personnel and an active recruitment network. We anticipate no issues with study recruitment beginning by the fifth month of the first year and continuing throughout the ninth month of the fifth year allowing for a total of 53 months. At a recruitment rate of approximately three participants per month, we should have no difficulty in completing the study in this time frame. Data analysis and manuscript preparation will take place during the last three months of the fifth year when recruitment has been completed.

PROTECTION OF HUMAN SUBJECTS

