1. RISKS TO THE SUBJECTS

1.1 Human Subject Involvement and Characteristics

Admission into the study is open to men and women and to all racial and ethnic groups, aged 18-65. We will scan 160 study participants including (1) cocaine-dependent (CD) individuals (n=80) and (2) healthy control (HC) subjects free of major Axis I diagnoses (n=80). Inclusion/exclusion criteria are listed below:

General Inclusion/Exclusion Criteria

Inclusion Criteria

1. Age 18-65.
2. Subjects must be able to provide informed consent and function at an intellectual level sufficient to allow accurate completion of all assessment instruments.
3. Subjects must consent to remain abstinent from all drugs of abuse (except nicotine) for the three-day period immediately prior to the study visit.
4. Subjects must consent to random assignment.
5. Subjects must have a negative breathalyzer, urine drug screen at the study visit.
6. Subjects must consent to the study visit which includes an outpatient visit to the ASD and completing one functional magnetic resonance imaging (fMRI) scanning session.

Exclusion Criteria

1. Subjects with evidence of or a history of significant hematological, endocrine, cardiovascular, pulmonary, renal, gastrointestinal, or neurological disease including diabetes.
2. Subjects with a history of or current psychotic disorder or bipolar affective disorder.
3. Subjects with current major depressive disorder or post-traumatic stress disorder.
4. Subjects taking any psychotropic medications, including SSRI's or other antidepressants, opiates or opiate antagonists. Subjects taking trazodone or non-benzodiazepene hypnotics for sleep will be included.
5. Women who are pregnant, nursing or of childbearing potential and not practicing an effective means of birth control.
6. Subjects who have a BMI that would preclude them from fitting comfortably in the scanner.
7. Persons with ferrous metal implants or pacemaker.
8. Subjects that are claustrophobic.
9. Subjects with significant psychiatric or medical problems that would impair participation or limit ability to complete the scanning session.
10. Subjects that require maintenance or acute treatment with any psychoactive medication including anti-seizure medications which could potentially interfere with fMRI data acquisition.

Group – Specific Inclusion/Exclusion Criteria

Individuals with Cocaine Dependence

Inclusion Criteria

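### The 45% attrition rate, 210 enrolled and 160 completed scans cannot all be right: 210 to 160 is about 24% attrition, and 160 scans at 45% needs about 291 enrolled

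*Combined protocol and SAP*

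**What the plan says.** The last sentence of Power and Sample Size, Specific Aim 1, reads: "To account for an estimated attrition rate of 45%, we will enroll 210 participants in order to complete 160 scans". It gives no source for the rate and no split between cocaine-dependent (CD) and healthy control (HC) participants.

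Elsewhere the target is consistently 160, or 40 in each of four groups:

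- Specific Aims plans 80 CD and 80 HC participants, with 40 per treatment group.
- C3b Participants says: "A total of 160 study participants will be recruited".
- C3f Statistical Methods expects 6 to 8 women per group, which is 15–20% of 40.
- Power and Sample Size, Specific Aim 2, says: "our proposed 40 participants per group should provide sufficient statistical power".
- Section 1.1 of Protection of Human Subjects says: "We will scan 160 study participants including (1) cocaine-dependent (CD) individuals (n=80) and (2) healthy control (HC) subjects" (also n=80).

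C3c anticipates screening about 350 people. C3i allows 53 months for recruitment and adds: "At a recruitment rate of approximately three participants per month, we should have no difficulty in completing the study in this time frame".

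**The concern.** The sentence ties the rate directly to the step from enrolment to completed scan, so any two of its figures fix the third. They do not fit.

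The 210 is the only enrolment figure offered to deliver the 40 per group on which the power statements rest. A reader cannot tell whether the rate, the enrolment or the expected number of scans is wrong. If the rate is right and 210 is treated as the enrolment total, each group would end about 28% smaller than planned.

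**Working it through.** **Inputs.** Attrition 45%, enrolment 210 and 160 scans (Power and Sample Size, Aim 1); 350 screened (C3c); 3 per month for 53 months (C3i). Effect sizes from Power and Sample Size: connectivity d = 0.9; craving 8.24/11.03 = 0.747; anxiety 1.07/2.20 = 0.486; Aim 2 effect 1.2.

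**Trying to reproduce 210 at 45%.**

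| Base for the 45% | N/(1 − 0.45) | N × 1.45 (common slip) |
|---|---|---|
| 160 scans | 290.9, so 291 | 232 |
| 140 (plan's independent-observations figure) | 255 | 203 |
| 135 (plan's printed clustered figure) | 246 | 196 |
| Loss among the 80 CD only, plus 80 HC | about 226 | 196 |

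None gives 210. Starting from 350 screened does not help: 1 − 210/350 = 40% and 1 − 160/350 = 54.3%, neither of which is 45%.

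**Solving for each figure in turn.**

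- Rate implied by 210 and 160: 1 − 160/210 = 23.8%. Rates of 24% and 25% give 211 and 214 enrolled.
- Enrolment implied by 45% and 160: 160/0.55 = 290.9, so 291, which is 291 − 210 = 81 more than stated.
- Scans implied by 45% and 210: 210 × 0.55 = 115.5, or 115.5/4 = 28.9 per group. The shortfall is 1 − 115.5/160 = 27.8%.

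**What about 29 per group would mean.** Two-sample t-test, noncentral t, two-sided 0.05, equal loss in CD and HC. The plan allows for repeated ratings through a design effect of 1 + (5 − 1) × 0.78 = 4.12 over five time points, so the credited figures multiply n by 5/4.12 (40 becomes 48.5; 29 becomes 35.2).

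| Comparison | 40 per group | 29 per group |
|---|---|---|
| Connectivity, d = 0.9 | 97.8% | 92.0% |
| Aim 2, 1.2 read as d | >99.9% | 99.4% |
| Craving, single measure | 91.0% | 79.8% |
| Craving, with repeated-measures credit | 95.4% | 87.1% |
| Anxiety, CD-OT vs CD-PBO, single measure | 57.5% | 44.5% |
| Anxiety, with credit | 66.0% | 52.1% |

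Reading 1.2 as d reproduces the plan's own Aim 2 figure: at n = 19 per group it gives 94.9%, against the stated .95.

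**If loss is unequal (assumed range).** Take 105 CD and 105 HC enrolled, with 45% lost overall. If CD lose 55%, each CD group is 105 × 0.45/2 = 23.6, and craving power is 71.0% (79.4% with credit). If CD lose 35%, each CD group is 105 × 0.65/2 = 34.1, and it is 86.0% (91.9% with credit).

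**Recruitment timetable.** Month 5 of year 1 through month 9 of year 5 is 8 + 36 + 9 = 53 months. 3 × 53 = 159, which fits 160 scans; 210 enrolled needs 210/53 = 4.0 per month. This does not show which figure is wrong, because C3i does not say whether the rate counts enrolments or scans.

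**The case against.** The arithmetic is not open to dispute, but its weight is. Nothing makes 210 a cap, and the sentence's stated purpose is to complete 160 scans. On the natural reading, enrolment continues until 160 are scanned, and no hypothesis, test or group size changes. The likeliest explanation may be one wrong planning percentage.

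Even the poor case is tolerable on the plan's own terms. Its formula, N_effective = nm/DE with m = 5, requires 140 × 4.12/5 = 115.4 participants, and 210 at 45% attrition yields 115.5. With d = 0.48 and CD and HC pooled within arm, that gives about 80.6% power for anxiety. (The printed 135 comes from 140 × 4/4.12 = 135.9, so it is not used as a benchmark here.) Connectivity and Aim 2 stay above 90%. Anxiety within CD is already short at 40 per group, which is a separate matter and adds no weight here.

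Most of this stands. Harm is conditional, the contradiction sits in one sentence, and the other sections merely repeat the 160 target. The unequal-loss range is an assumption with no support in the documents. What the objection does not do is make the three figures agree or say which to believe. The pooled calculation is also not the comparison in Hypothesis 1C, which is within CD only.

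**Conclusion.** The concern holds. The rate, the enrolment and the number of scans are mutually inconsistent, and no alternative base that was checked reconciles them. The document does not reveal which is wrong.

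The consequence for power is conditional on three things: 45% being correct, accrual stopping at 210, and equal loss in CD and HC. Under those conditions about 115 participants are scanned, roughly 29 per group. Connectivity and Aim 2 remain well powered; craving falls to 80% on a single measure, or 87% with the repeated-measures credit. Damage to the conclusions is not shown. This should be fixed because enrolment planning relies on the figure, but it does not undermine the design.

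**What to change.** Make the three figures agree and state the basis for the attrition rate. The sponsor must say which figure is in error.

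1. **Correct the rate to about 24%**, if recruitment experience supports it, keeping 210 and 160. This changes one figure in Power and Sample Size, Aim 1, and adds no participants.
2. **Keep 45% and 210**, state an expected yield of about 115 scans and restate power at about 29 per group. The 160 and 40-per-group statements in Specific Aims, C3b, C3f Statistical Methods, both Power and Sample Size parts and section 1.1 must then follow. Women per group become about 4 to 6 (15–20% of 28.9). This adds no participants, but it lowers the declared target and the stated power.
3. **Keep 45% and 160**, in which case the enrolment figure must read about 291. This costs about 81 more enrolments than stated.

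Two clarifications of a few words each would also help, though neither is a further error: whether C3b's 160 counts people enrolled or scanned, and whether C3i's three per month does.
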